14.2. Sample Size Justification

The study is designed and powered to demonstrate non-inferiority of the Test lens relative to the Control 1 with respect to night driving performance score. Assuming no difference between Test and Control 1, the sample size was calculated using a non-inferiority margin of -0.25. The sample size of 24 subjects is considered sufficiently large to test for non-inferiority with a minimum power of 80% and a two sided type I error of 0.05. The plan is to enroll 28 eligible subjects with a target completion of 24 subjects. During the enrollment period, the subject dropout rate will be closely monitored, if unexpectedly high dropout rate is observed, the targeted total enrollment number will be increased accordingly in order to ensure a minimum of 24 subjects per group to complete the study.

The non-inferiority margin and sample size calculations were based on available historical data from 6 published papers between 2009 and 2015 and from an investigator initiated study (IIS) sponsored by JJVC in 2016 that examined the effect of vision condition on driving performance. The table below summarized the studies considered in the meta-analysis

After categorizing the vision condition of the study groups into a binary variable as corrected and uncorrected, a Bayesian random effect meta-regression model was conducted on the pooled data to evaluate the overall effect of uncorrected vision on driving performance. The model can be written as

$$y_{ij} | \mu_{ij} = \mu_{ij} + e_{ij}; \text{ with } e_{ij} \sim N(0, s_{ij}^2)$$

$$\mu_{ij} = \mathbf{X}_{ij}\boldsymbol{\beta} + \delta_{ij}; \text{ with } \delta_{ij} \sim N(0, \sigma^2)$$

Here y_{ij} is the driving performance in vision condition group i in study j , \mathbf{X}_{ij} is a vector of covariates from the i^{th} vision condition group and j^{th} study and $\boldsymbol{\beta}$ is the vector of regression coefficients. The term δ_{ij} is the random effect due to the between study variation while s_{ij}^2 represents the within study variation (known). The regression model included vision condition (corrected vs. uncorrected) and the covariates: driving time (day, night, day & night), average age and indicator variables of whether or not cone gap perception (not used in this study), course time and hazard avoidance were included in the calculation of the driving performance composite score.

We used independent vague normal $N(0,1000)$ priors for the regression coefficients $\boldsymbol{\beta}$, vague inverse-gamma with shape and scale parameters of 0.001 for the variance parameter σ^2 . The Metropolis sampler algorithm as implemented in the SAS MCMC Procedure (SAS/STAT 14.1, SAS Institute, 2015) was used to carry out parameter estimation. After a burn-in of 80,000 iterations, we run the algorithm for additional 500,000 iterations with a thinning factor of 100 to allow posterior chains of estimated parameters to converge. Convergence of the simulated chains was assessed using autocorrelation and sample trace plots.

The posterior mean difference in driving performance between corrected and uncorrected vision was estimated to be 0.579 with 95% credible interval (95% CrI) of (0.249, 0.917). The estimated variance was 0.0483 with 95% CrI of (0.0051, 0.1692).

With a sample size of 24 subjects, the estimated power for different scenarios of intra-class correlation (ICC) is shown in the table below:

Table 5: Statistical Power by ICC

Intra-class correlation (ICC)	Between subject variance σ^2	Effect size	Power (%)
.40	0.05	0.25	71
.50	0.05	0.25	85
.60	0.05	0.25	95

The sample size calculation was conducted using the PROC POWER Procedure (SAS/STAT 14.1, SAS Institute, 2015). The non-inferiority hypothesis testing problem of a 3x3 crossover design was formulated as a two-sample non-inferiority hypothesis testing (Peng Sun, 2010).

As discussed above, the estimated posterior mean difference in driving performance between corrected vision (treated) and uncorrected vision (untreated) was estimated to be 0.579 with 95% credible interval (95% CrI) of (0.249, 0.917). We therefore used the lower bound of the 95% credible interval as the non-inferiority margin (\sim -0.25). This represents a discount of 43% from the estimated difference between corrected vision and uncorrected vision.

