14.4. Level of Statistical Significance

All planned analysis will be conducted with an overall type I error rate of 5% for the primary and secondary hypotheses. Unless otherwise specified, all statistical tests will be 2-sided.

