14.5. Primary Analysis

Overall Driving Performance score

Overall driving performance score will be analyzed using a linear mixed model; sequence of lens wear, period, lens type, first order carry-over, driving time (day or night) and the interactions between lens type by driving time and period by driving time will be included in the model as fixed effects. Age will be included as fixed covariate when appropriate. An appropriate covariance structure will be selected to model the correlation between measurements across periods within the same subject and driving time. Covariance structures that will be considered include:

- Compound Symmetry (CS)
- Heterogeneous Compound Symmetry (CSH)
- Unstructured (UN)
- Ante-dependence (ANTE(1))

For ANTE(1) structure, subject and driving time nested within subject will be included in the model as random effects. For the remaining structures only subject will be included as random effect. The covariance structure that returns the lowest Akaike Information Criteria Corrected

(AICC) will be selected as the structure that best fit the data¹¹. Heterogeneous residuals covariance structures (R-side) across driving time will be considered when appropriate. The log-likelihood ratio test will be used to test for the homogeneity between the residual covariance structures. The Kenward and Roger method will be used for the denominator degree of freedom.

Comparisons between Test and Control 1 will be conducted overall across driving time and within each level of driving time. Results from the final selected model will be reported as least-square mean (LSM) differences with 95% confidence intervals.

The null and alternative hypotheses for non-inferiority of Test lens relative to Control 1 are as follows:

$$\begin{aligned} H_0: \mu_T - \mu_C &\leq -0.25 \\ H_A: \mu_T - \mu_C &> -0.25, \end{aligned}$$

where μ_T and μ_C are the means of night driving performance score for Test and Control 1, respectively. Non-inferiority of the Test relative to Control 1 will be concluded if the lower limit of the 95% confidence interval of the LSM difference between Test and Control 1, at night driving time, is greater than - 0.25.

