1.5. Sample Size Justification

The study is designed and powered to demonstrate non-inferiority of the Test lens relative to the Control 1 lens with respect to night driving performance score. Assuming no difference between the Test and Control 1 lens, the sample size was calculated using a non-inferiority margin of -0.25. The sample size of 24 subjects is consider sufficiently large to test for non-inferiority with a minimum power of 80% and a two-sided type I error of 0.05. The plan is to enroll 28 eligible subjects with a target completion of 24 subjects. During the enrollment period, the subject dropout rate will be closely monitored, if an unexpectedly high dropout rate is observed, the target enrollment will be increased accordingly to ensure a minimum of 24 subjects per group complete the study.

The non-inferiority margin and sample size calculations were based on available historical data from 6 published papers between 2009 and 2015 and from an investigator initiated study (IIS) sponsored by JJVC in 2016 that examined the effect of vision condition on driving performance. The Table below summarizes the studies considered in the meta-analysis.

I able 1: Summary of published papers considered in the meta-analysis Sample Age Driving Study Vision							
Year	Author	Paper Title	Sample Size	Age (Mean)	Driving Time	Study Group	Vision Condition
						Young	Corrected
						Middle-Age	Corrected
		Age and Visual				Older	Uncorrected
2002	Wood, JM	Impairment Decrease Driving Performance as	139	57.4	Day & Night	Older with ocular disease	Uncorrected
		Measured on a Closed-Circuit Road				older with moderate / severe ocular disease	Uncorrected
		Effects of Age				Young	Corrected
2005	Chaparro, A. et al.	Auditory and Visual Dual Tasks on Closed-Road Driving Performance	28	48.3	Day	Older	Uncorrected
2006	Wood,	Bilateral cataract	47	71.1	D	Normal vision	Corrected
2006	JM. et al.	surgery and driving performance	47	71.1	Day	Cataract	Uncorrected
	Wood, JM. et al.	Interaction between visual status, driver age and distracters on daytime driving performance	39	47.9		Normal vision	Corrected
2009					Day	Blur	Uncorrected
						Cataract	Uncorrected
	Wood, JM. et al.	Effects of Simulated Visual Impairment on Nighttime Driving Performance	20	27.5	Night	Normal vision	Corrected
2010						Refractive blur	Uncorrected
						Simulated cataract	Uncorrected
2012	Wood,	Useful Field of View Predicts Driving in	02	73.6	Day	Driving without visual distraction	Corrected

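### The power tables fit a one-sided 5% test, not the stated two-sided 5% level and 95% interval rule; alpha and variance formula should be corrected together

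*Protocol*

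**What the plan says.** Protocol 14.2 sets the level and the target: 24 subjects are enough "to test for non-inferiority with a minimum power of 80% and a two sided type I error of 0.05". SAP 1.5 repeats this ("with a minimum power of 80% and a two-sided type I error of 0.05"). The calculation is described as "Assuming no difference between Test and Control 1", and "the sample size was calculated using a non-inferiority margin of -0.25".

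Protocol Table 5, repeated as SAP Table 2, is introduced with "With a sample size of 24 subjects, the estimated power for different scenarios of intra-class correlation (ICC) is shown in the table below". It gives 71, 85 and 95% for ICC 0.40, 0.50 and 0.60, each with a variance of 0.05 (labelled between-subject) and an effect size of 0.25. Both documents say that the 3x3 crossover problem was handled as a two-sample non-inferiority test in PROC POWER.

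On the level of testing, Protocol 14.4 adds: "Unless otherwise specified, all statistical tests will be 2-sided". Under Protocol 14.5, non-inferiority is "concluded if the lower limit of the 95% confidence interval of the LSM difference between Test and Control 1" at night exceeds -0.25, and SAP 5.2 has the same rule. Neither document mentions a one-sided 5% level or a 90% interval.

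**The concern.** A lower 95% limit compared with a margin is a one-sided 2.5% test, which agrees with the stated two-sided 0.05. The power table should describe that test. If it was run at one-sided 5%, it allows twice the error rate of the decision rule, and the statement about at least 80% power rests on figures for a different test.

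The ICC 0.50 row matters most. It is printed at 85%, and it falls below 80% if the two-sample formulation is kept and only alpha is corrected. The documents give no evidence for any particular ICC, so the ICC at which the 80% claim starts to hold is material to a reader.

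**Working it through.** **Inputs.** Margin 0.25, true difference 0, 24 completers, variance 0.05 (rounded from the meta-regression estimate of 0.0483), ICC 0.40, 0.50 and 0.60, two-sample formulation: all from Protocol 14.2. Decision level: one-sided 2.5%, from the 95% interval rule in Protocol 14.5.

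**Step from ICC to variance (inferred, not printed).** If 0.05 is the between-subject variance, then ICC = 0.05/(0.05 + sw2), so sw2 = 0.05 × (1 − ICC)/ICC:

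- ICC 0.40: 0.05 × 0.60/0.40 = 0.075
- ICC 0.50: 0.05 × 0.50/0.50 = 0.050
- ICC 0.60: 0.05 × 0.40/0.60 = 0.0333

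**Standard error, two-sample formulation.** SE = sqrt(4 × sw2/24). This is 24 per group with SD sqrt(2 × sw2), 46 df. Twelve per group with SD sqrt(sw2) has the same SE on 22 df.

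- ICC 0.40: sqrt(0.0125) = 0.1118, and 0.25/0.1118 = 2.236
- ICC 0.50: sqrt(0.00833) = 0.0913, and 0.25/0.0913 = 2.739
- ICC 0.60: sqrt(0.00556) = 0.0745, and 0.25/0.0745 = 3.354

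These ratios are the noncentrality parameters. Power is the probability that a noncentral t exceeds the one-sided critical value.

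| Two-sample formulation | ICC 0.40 | ICC 0.50 | ICC 0.60 |
|---|---|---|---|
| Printed in the plan | 71 | 85 | 95 |
| One-sided 5%, 46 df | 71.2 | 85.4 | 95.1 |
| One-sided 5%, variance 0.0483, 22 df | 71.2 | 85.4 | 95.2 |
| One-sided 5%, variance 0.05, 22 df | 69.9 | 84.3 | 94.6 |
| One-sided 2.5%, 46 df | 59.1 | 76.5 | 90.7 |
| One-sided 2.5%, variance 0.0483, 22 df | 58.5 | 75.9 | 90.3 |
| One-sided 2.5%, variance 0.05, 22 df | 57.1 | 74.5 | 89.3 |

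Two set-ups at one-sided 5% reproduce all three printed figures after rounding. At one-sided 2.5% the same set-ups fall about 4 to 14 points short (95 − 90.7 = 4.3 at the least, 71 − 57.1 = 13.9 at the most).

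**Could another set-up give the table at one-sided 2.5%?** With the effective sample size left free, the best fit at 2.5% still misses by 1.1 points and needs about 16 per group (exactly 16 per group gives 70.5, 86.4 and 96.3). Nothing in the documents supports 16 per group. The best fit at 5% misses by about 0.15 points, at essentially 12 per group, or 24 in total. Reading 0.05 as the total variance misses by about 5 points or more at either level.

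**ICC needed for 80% in the two-sample formulation.** About 0.46–0.47 at one-sided 5%, and about 0.52–0.53 at one-sided 2.5%.

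**The contrast that will be analysed.** The primary model estimates a within-subject difference. Without carry-over its variance is 2 × sw2/24, half of the 4 × sw2/24 above. Fitting first-order carry-over in this six-sequence design multiplies that by 1.25, giving 2.5 × sw2/24.

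| Crossover contrast, one-sided 2.5%, 44 df | ICC 0.40 | ICC 0.50 | ICC 0.60 |
|---|---|---|---|
| Without carry-over | 87.1 | 96.6 | 99.6 |
| With carry-over (factor 1.25) | 79.0 | 92.3 | 98.6 |

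The printed 71, 85 and 95% match neither the two-sample formulation at the stated level nor the crossover contrast at that level.

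**The case against.** The strongest reply is that the trial is decided by a within-subject crossover contrast. With the plan's inputs at the correct level, that contrast has more power than the table prints in every row, even with carry-over fitted. A reader might infer from the alpha mismatch that every printed power is too high for the deciding test, or that the trial is underpowered. The documents support neither. Halving the variance outweighs the loss from one-sided 5% to one-sided 2.5%. The overstatement exists only within the two-sample formulation that the plan chose.

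It also stands that the reconstruction is inferred. The step from ICC to variance, the number per group and the degrees of freedom are not printed. The tabulated 0.05 with a literal 12 per group on 22 df rounds to 70, 84 and 95, not to the table. An exact match needs either 24 per group with doubled variance or the unrounded 0.0483. The defensible statement is that the table is consistent with one-sided 5%, not that a particular program call has been proved.

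Finally, the 95% interval rule is sound, so type I error and the primary conclusion are not affected.

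What the reply does not do is rescue the table. Two departures in opposite directions do not make a justification that can be reproduced at its stated alpha.

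**Conclusion.** The concern holds as a fault in the sample-size justification. Protocol Table 5 and SAP Table 2 fit a one-sided 5% test under the plan's two-sample formulation and do not fit the stated level or the 95% interval rule. At the stated level that formulation gives about 57–59, 75–77 and 89–91%, and two of the three rows then miss 80%. Whatever the alpha, the ICC 0.40 row as printed (71%) already contradicts the claim of at least 80%.

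Adequacy of the sample size is a separate question. If the variance of 0.05 and the ICCs are accepted, the analysed contrast has about 92% power at ICC 0.50, 99% at 0.60, and is borderline at 0.40 (79%) with carry-over fitted.

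These results assume sw2 = 0.05 × (1 − ICC)/ICC, a true difference of zero, 24 completers and, for the carry-over figures, a variance factor of 1.25. Severity: should-fix.

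**What to change.** Recompute Protocol Table 5 and SAP Table 2 at one-sided 0.025, using the variance of the Test versus Control 1 crossover contrast that will be analysed, with carry-over included. Beside each table, print the alpha, the variance formula and the step from ICC to within-subject variance. Replace the sentence claiming at least 80% power with the resulting figures and the ICC on which each depends.

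Alpha should not be changed alone. That would print about 57–59, 75–77 and 89–91% from a formula with twice the variance of the contrast, and would wrongly suggest a shortfall at ICC 0.50.

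Keep the 95% interval decision rule and the sample size unchanged. The cost is one recalculation and matching text in two documents, with no design change and no added subjects.

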2.2. Endpoints

2.2.1. Primary Endpoint(s)

Overall driving performance score

A closed road driving circuit environment will be used to evaluate the effects of the Test lens on night and day time driving performance. This approach involves driving a real vehicle on a closed road circuit (closed to all traffic except [REDACTED] vehicles), the driving environment can be modified to closely resemble real on-road conditions and safety can be assured. Quantitative methods will be used to assess vision and driving performance under a range of challenging conditions and appropriate masking, order of testing, randomization and control conditions will be used.

Overall driving performance score is a composite score calculated as the mean of the Z-scores of the following six driving measures: average sign recognition distance (in meters), percentage of correctly identified sign (~42 signs), percentage of hazard avoidance/detection (9 hazards), average pedestrian recognition distance (in meters), lane keeping (percentage of time inside the lane) and the inverse of driving lap time (in seconds).). Equal weighting will be assigned to each measure. Where necessary the individual Z scores will be transformed (inverted) such that positive Z scores relate to better performance than the mean. This approach captures participants' performance relative to the group as a whole across conditions and takes into consideration the fact that some tasks may be prioritized over others during driving (Wood JM.; 2002).

Overall driving performance will be calculated for each participant by test article (Test, Control 1 and Control 2) and driving time (day and night).

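### The power table uses the meta-regression's between-study variance as a between-subject variance, so the stated power for N = 24 has no support

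*Protocol*

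**What the plan says.** Protocol 14.2 models the driving performance of each vision-condition group in each historical study. The model has two sources of scatter. One is the within-study variance, which is treated as known. The other is a term δ with variance σ², which "is the random effect due to the between study variation". Only σ² receives a variance prior. The result reads "The estimated variance was 0.0483 with 95% CrI of (0.0051, 0.1692".

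Table 5 follows directly. Its second column is headed "Between subject variance", carries the symbol σ² again, and holds 0.05 in every row. With effect size 0.25, power is given as 71%, 85% and 95% at ICC .40, .50 and .60. The text states "Assuming no difference between Test and Control 1, the sample size was calculated using a non-inferiority margin of -0.25" and calls 24 completers sufficient "with a minimum power of 80% and a two sided type I error of 0.05". SAP 1.5 repeats the model, the estimate and the table (as Table 2).

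The endpoint being powered is a "composite score calculated as the mean of the Z-scores of the following six driving measures" (Protocol 2.2.1), compared between Test and Control 1 at night. On the decision rule, Protocol 14.5 says: "Non-inferiority of the Test relative to Control 1 will be concluded if the lower limit of the 95% confidence interval" of the least-squares mean difference exceeds the margin.

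**The concern.** The precision of the night comparison of Test with Control 1 depends on how much one driver's score varies from run to run. The plan obtains that within-subject variance from a between-subject variance and an assumed ICC. The number used as the between-subject variance is the scatter of group averages across historical studies that differed in age, ocular disease, simulated cataract, blur and distraction (SAP Table 1). That scatter does not measure how individual drivers differ within one trial, nor how one driver differs between runs.

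This calculation is the only justification given for 24 completers on the primary non-inferiority test. If its variance input is a different quantity, the reader cannot tell whether the study has the power claimed.

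**Working it through.** **Inputs.** From Protocol 14.2: margin −0.25, true difference 0, 24 completers, ICC .40/.50/.60, σ² = 0.0483 (limits 0.0051 and 0.1692) or its rounded value 0.05. From Protocol 14.5: a 95% interval rule, which is one-sided 2.5%.

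**Step 1: which variance is 0.0483?** The within-study variances are known and so are not estimated. The only variance the model estimates is σ², the between-study term. Hence 0.0483 is heterogeneity of group means.

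**Step 2: reproduce the table.** Within-subject variance: σw² = σ²(1 − ICC)/ICC. Two-sample layout with 12 per group: SE = √(2σw²/12). Power comes from the noncentral t with df 22 and noncentrality 0.25/SE, at one-sided 5%. With σ² = 0.0483:

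| ICC | σw² | SE | 0.25/SE | Power | Printed |
|---|---|---|---|---|---|
| .40 | 0.0725 | 0.110 | 2.27 | 71.2% | 71% |
| .50 | 0.0483 | 0.090 | 2.79 | 85.4% | 85% |
| .60 | 0.0322 | 0.073 | 3.41 | 95.2% | 95% |

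The match is not unique. Using 0.05 with 24 per group and variance 2σw² (the same SE formula, df 46) also rounds to 71/85/95%. Either way, the printed power follows from this one number. Of the layouts tried, only those at one-sided 5% reproduce the table. At one-sided 2.5%, 12 per group with 0.05 gives 57/74/89%.

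**Step 3: sensitivity to the input.** Same formula as in the table (12 per group, df 22, one-sided 5%), at the plan's own credible limits:

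| σ² | ICC .40 | ICC .50 | ICC .60 |
|---|---|---|---|
| 0.0051 | about 100% | about 100% | about 100% |
| 0.1692 | 32% | 42% | 55% |

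In this layout, 80% power needs σw² of at most 0.057. Nothing in either document lets a reader check that value.

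**Step 4: the contrast actually planned.** In a six-sequence design with 24 subjects (4 per sequence) and carry-over in the model, the Test minus Control 1 contrast has variance 0.1042σw² with df 42, taking the night data alone with a common within-subject variance. At one-sided 2.5% and σ² = 0.05, power is 79/92/99%. Here 80% power needs σw² of at most 0.073. The more efficient contrast and the stricter alpha pull in opposite directions, and the result still depends on the unsupported 0.05.

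**Step 5: a conditional check against the endpoint.** If each of the six Z-scores had variance 1 within night runs, with mean correlation r between components, the composite would have variance (1 + 5r)/6. For r ≥ 0 that is at least 1/6 = 0.167. The table implies total variances of 0.05/ICC:

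- ICC .40: 0.05/.40 = 0.125
- ICC .50: 0.05/.50 = 0.100
- ICC .60: 0.05/.60 = 0.083

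All three lie below 0.167. However, if Z-scores are standardised over day and night together, and the two differ by d standard deviations on each measure, the night variance shrinks by the factor 1 − d²/4. With r = 0, d = 1 gives 0.167 × 0.75 = 0.125, and d = 1.41 gives 0.167 × 0.50 = 0.083. The implied totals can therefore be reached.

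**The case against.** Four points can be made for the plan.

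- **The link is not stated in words.** Neither document says that 0.05 came from 0.0483, and the table reproduces from either figure. That is true. But the shared symbol, the rounded value, the statement that the calculations rest on this historical data, and the absence of any other source leave no other reading that the text supports.
- **The power may be adequate.** A reader might infer that the trial is shown to be underpowered. The documents do not support that. The low figures at 0.1692 have a counterpart of about 100% at 0.0051, and the planned contrast with 0.05 gives 79/92/99%, at least as high as the table. This stands: the power is unsupported, not shown to be too low.
- **There is no proven clash with the endpoint.** A reader might infer that the table contradicts the Z-score definition, because a mean of six unit-variance scores cannot have a variance as small as 0.083 without negative correlations. That holds only with unit variance within night runs. Protocol 2.2.1 describes performance relative to the whole group across conditions, which suggests pooled standardisation. Because drivers may trade one task against another, correlations near or below zero cannot be ruled out either. This also stands, so step 5 is supporting evidence at most.
- **Inference is not affected.** The margin, the model and the interval rule do not use this variance, so the mislabelling cannot by itself produce a false claim of non-inferiority. That is correct. What is at stake is the justification of the sample size.

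**Conclusion.** The point holds as a finding about justification. A between-study variance of group means, 0.0483, appears in Protocol Table 5 and SAP Table 2 as a between-subject variance of 0.05, and the within-subject variance is derived from it. The two are different quantities, and no subject-level variance is cited. The figures of 71/85/95% and the statement of at least 80% power are therefore unsupported.

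No corrected power can be given, because the documents contain no variance from which to compute one. On the plan's own credible interval, the table's formula spans about 100% down to 32/42/55%, and the direction of the error is unknown. This range assumes the layout that reproduces the table: 12 per group at one-sided 5%. That the table draws on 0.0483 is inferred from symbol, value and lack of another source, not from an explicit statement.

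**What to change.** In Protocol 14.2 and SAP 1.5:

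1. Label 0.0483 as between-study heterogeneity and remove it from the power calculation.
2. Replace it with a within-subject variance of the night composite score, with its source. The sponsor-funded 2016 night-driving study in SAP Table 1 is one candidate, if its subject-level data are accessible; the documents do not say that the sponsor holds them. It had 10 subjects, so a variance on about 9 df has a 95% interval of roughly 0.47 to 3.3 times the estimate. Its composite may also have used different components. If no suitable data exist, state the variance as an assumption and show power over a range.
3. State how the Z-scores are standardised (night alone, or day and night together), so that the assumed variance can be checked against the endpoint.
4. Recompute both tables at one-sided 2.5%, to match the 95% interval rule, and reword the 80% sentence to agree with the result. The present table's own first row is 71%.

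The cost is a re-run of the calculation and new wording in two sections, with no extra subjects. The downside is that the stated power may become less favourable or have to be given as a range.
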